- Group 2: secukinumab 150 mg (1mL) once every four weeks till (and including) Week 256. After approval and implementation of Amendment 1, patients may be escalated to 300 mg as judged appropriate by the investigator.

Study treatment dose adjustments are not permitted until Week 156.

Starting from Week 156 (i.e. during the open label study period), after approval and implementation of Amendment 1, the secukinumab dose should be escalated from 75 mg to 150 mg for patients whose signs and symptoms are not fully controlled with the current dose of 75 mg, and may improve with higher dose as judged by the investigator.

Further, the dose should also be escalated to 300 mg for patients currently on 75 mg or 150 mg, and whose signs and symptoms are not fully controlled and may improve further with an increase in dose as judged by the investigator.

Dose escalation from secukinumab 75 mg to 300 mg can be done either in one step or in two steps (first 150 mg, then 300 mg based on investigator's judgement).

For patients escalated to 150 mg or 300 mg, no dose reduction can be performed at a later stage.

Subjects will continue to be on background methotrexate (MTX) (if they were already taking MTX at the start of core study CAIN457F2306) throughout the study. The dose of MTX may be adjusted as deemed appropriate by the investigator.

In addition subjects will be allowed to start or adjust the dose of corticosteroids and non-steroidal anti-inflammatory drugs (NSAIDs) as deemed appropriate by the investigator.

[figure not shown]
Before enrolment in this extension study, all subjects electing to continue will sign an Informed Consent form. After approval and implementation of Amendment 1, all subjects electing to continue will sign a new version of the Informed Consent form. Detailed instructions for self-administration of the s.c injection using the PFS formulation will be provided to each subject. Each injection will be administered into an appropriate injection site of the body. For the first 6 months of the extension study (up to Week 128), all injections will be performed at site. Starting from Week 132 subjects will have the choice of self-administration at home or continuing with administration at site, based on personal preference and the investigator's clinical judgment. Site staff or caregiver (once trained) will administer the injection to subjects who are not able or feel insecure to self-administer the PFS injection.

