5.5.5 Permitted dose adjustments and interruptions of study treatment

Study treatment dose adjustments are not permitted until Week 156.

After approval and implementation of Amendment 1, patients previously treated with secukinumab 75 mg may receive either 75 mg, 150 mg or 300 mg, and patients previously treated with secukinumab 150 mg may receive 150 mg or 300 mg, as deemed appropriate by the investigators. The decision may be taken at any on-site visit. When dose escalation has been performed for one patient, no dose reduction can be performed at a later stage.

Study treatment interruption is also not permitted with the following exceptions:

- Study treatment interruption is permitted only if, in the opinion of the investigator, a subject is deemed to be placed at a significant safety risk unless dosing is temporarily interrupted. In such cases study treatment should be interrupted only during the time that this risk is present and ongoing. Study treatment can be restarted at the next scheduled visit after resolution of the safety risk.
- The effect of secukinumab on live vaccines is unknown; therefore live vaccines should not be administered during participation in the study. In case a live vaccine has been

administered due to a medical urgency, study treatment should be interrupted for 12 weeks.

The reason for any study treatment interruption must be recorded on the corresponding eCRF page.

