5.5.11 Study completion and post-study treatment

A subject will be considered to have completed the study if he/she received treatment for 260 weeks in the combined core study and extension study (last dose being administered at Week 256) and upon completion of the scheduled study assessments and procedures up to and including Visit F268.

Information on the subject's completion or discontinuation of the study and the reason for discontinuation of the study will be recorded on the appropriate Study Phase Completion eCRF page.

A Study Phase Completion evaluation (associated with the last visit of the subject's phase of the study: e.g. Week 156, Week 208 or Week 260) must also be performed when a subject prematurely withdraws from the study for whatever reason. In any case, the investigator or site staff must contact the IRT as soon as possible to record the subject's study completion (Visit F268) and/or discontinuation.

The investigator must provide follow-up medical care for all subjects who are prematurely withdrawn from the study, or must refer them for appropriate ongoing care. This care may include another treatment outside of the study as deemed appropriate by the investigator. This treatment may be any non-biologic DMARD. In case of a biologic treatment, a waiting period of 3 months before initiating the treatment is recommended.

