12.4 Analysis of Primary Variable(s)

The primary efficacy variable(s) is the clinical response to treatment according to ACR20, ACR50 and ACR 70 improvement in disease activity over time up to Week 260.

ACR response criteria denote the response (i.e., improvement) in signs & symptoms of the disease of a subject compared to baseline of the core study.

The analysis of the primary variables will be based on the FAS. Primarily, CRP will be used instead of ESR to calculate ACR response; ESR will only be used in the event CRP is missing.

Shift tables will be provided comparing the subject's ACR evaluation at the pre up-titration visit relative to the observed data of the following week intervals after up-titration: (12-32 weeks), (36-56 weeks) and (60-80 weeks). The ACR grouping presented in the table will be: $ACR < 20$, $20 \leq ACR < 50$, $50 \leq ACR < 70$, $ACR \geq 70$.

Graphical representation (line plots) of ACR20, ACR50 and ACR70 response over time and Sankey-style bar chart for the ACR response within the subjects that up-titrated from 150 mg to 300 mg (provided that up-titration has been occurred for more than 8 weeks) will be drawn from the observed data.

Additionally, observed data tables will summarize the ACR20, ACR50 and ACR70 response following up-titration when assessed. Results will be illustrated in line plots.

Also individual subject listings of the ACR components as well as for the ACR20/50/70 response will be given.

Statistical model, hypothesis, and method of analysis

No formal hypotheses are planned for this study. The proportion of subjects meeting the ACR criteria (ACR20, ACR50, and ACR70) will be descriptively summarized for each treatment by absolute and relative frequencies followed by 95% confidence intervals for the proportion of patients responding to treatment according to the ACR criteria from Week 1 onwards based on the pooled data from core and extension study. Results regarding ACR20/50/70, will be presented overall in the FAS population as well as in subgroups by TNF α status (naive or IR) and by concomitant use of MTX as appropriately.

Placebo group (core study) in efficacy analysis will not be considered.

All the above efficacy variables will be analyzed on the FAS (unless otherwise specified) for all applicable analysis visits based on the observed data.

For binary variables, the proportion of responders along with the 95% CI will be presented by treatment groups over analysis visits.

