For continuous variables, the change from baseline (of core) when available, will be summarized.

[REDACTED]

Figures will be provided for the following parameters:

- [REDACTED]
- DAS28-CRP and SF-36 PCS change from baseline.
- HAQ-DI score (change from baseline) overall and following the up-titration
- HAQ-DI response overall and following the up-titration
- HAQ-DI response by TNF- α inhibitor status.
- Remission response and low disease activity response according to DAS28-CRP
- [REDACTED].
- [REDACTED]

Individual listings will be considered for all efficacy variables of the study.

Joint/bone structural damage at Week 156, 208

The changes in joint/bone structural damage (total sharp score, and its components, erosion score and joint spacing narrowing score) will be summarized by the same treatment groups as follows using evaluable data of each x-ray reading session:

- Baseline to:
 - Week 24
 - Week 52
 - Week 104
 - Week 156
 - Week 208
- Week 24 to:
 - Week 52
 - Week 104
 - Week 156

[figure not shown]
- Week 208
- Week 52 to:
 - Week 104
 - Week 156
 - Week 208
- Week 104 to:
 - Week 156
 - Week 208

[figure not shown]
[figure not shown]
The above analyses will be done on both FAS and X-ray completers where X-ray completers are those subjects that had X-ray measures at baseline, Week 16/24, Week 52, Week 104, Week 156 and Week 208. Subgroup analyses by TNF-alpha inhibitor status will be provided.

Analyses will be performed for each reading campaign, as appropriate depending on the available data.

For the purpose of the campaign 3 the readings of baseline, week 156 and week 208 will be used for the analysis. Any data on week 260 will be shown only in listings.

Individual listings will be provided for Joint structural damage components.

13 Pharmacokinetic evaluations (change / add PD, PK/PD, Biomarkers, as needed)

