No visit windows were used in case of up-titrations. The before up-titration measurement is considered as the last visit measurement, performed on or before the date that patient took the up-titration dose. The up-titration data analysis will be based on week intervals; it is accounting for the time period between the actual date of exposure to the up-titrated dose and the last visit date of the subject:

- 4 – 8 weeks after up-titration
- 12 – 32 weeks after up-titration
- 36 – 56 weeks after up-titration
- 60 – 80 weeks after up-titration
- 84 – 104 weeks after up-titration

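### ACR and HAQ-DI results by time since up-titration rest on progressively earlier escalators, so a trend can appear from the changing cohort alone

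*SAP*

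**What the plan says.** **Outputs.** SAP 12.4 specifies for ACR that "observed data tables will summarize the ACR20, ACR50 and ACR70 response following up-titration when assessed. Results will be illustrated in line plots". For HAQ-DI it lists figures only, among them "HAQ-DI response overall and following the up-titration" and the change in score after up-titration. It names no HAQ-DI table and no plot type.

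**Time axis.** SAP 17.1 says "The up-titration data analysis will be based on week intervals": 4–8, 12–32, 36–56, 60–80 and 84–104 weeks. The reference is the last measurement on or before the first up-titrated dose.

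**Subjects and data.** The up-titration subset (SAP 5) needs one up-titrated dose and no minimum follow-up. SAP 12.3 uses observed data, without multiple imputation or MMRM.

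**When escalation can happen.** Protocol 5.5.5: "Study treatment dose adjustments are not permitted until Week 156", and thereafter "The decision may be taken at any on-site visit". Protocol 3.1 adds the condition "Starting from Week 156 (i.e. during the open label study period), after approval and implementation of Amendment 1". The trigger is the investigator's view, for example of "patients whose signs and symptoms are not fully controlled with the current dose of 75 mg".

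**When assessment ends.** Protocol 5.5.11 describes completion with the "last dose being administered at Week 256". In Table 6-3 the last joint counts and HAQ-DI are at Week 260. The Week 268 follow-up visit has neither.

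**Pairing already planned.** SAP 12.4 gives ACR shift tables against the pre-up-titration visit for 12–32, 36–56 and 60–80 weeks.

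**The concern.** Start of escalation is staggered over about two years and the end of assessment is common to everyone, so available follow-up is 260 minus the escalation week. Each successive interval loses the most recent escalators. Escalation follows a judgement about disease control, so early and late escalators may well differ in response. If they do, a line joining the intervals mixes two things: what happens to subjects on the higher dose, and which subjects are still in the picture.

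Amendment 1 justifies escalation by the wish to keep a high proportion of meaningful responses for the whole extension. A plot of ACR response against time since escalation invites a reading in just those terms. The absence of a hypothesis test does not protect a descriptive figure from this artefact.

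**Working it through.** **Inputs**
- Scheduled site-dosing visits from Week 156 (Protocol Tables 6-1 to 6-3): 156, 168, 180, 192, 208, 220, 232, 244.
- Scheduled ACR and HAQ-DI assessments after Week 156: 180, 208, 232, 260.
- Intervals: SAP 17.1.

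**The plan's own figure.** Longest possible follow-up after escalation = 260 − 156 = 104 weeks. This matches the upper end of the last SAP interval.

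**Latest start that can reach each interval** = 260 minus the lower bound: Week 256 for 4–8, 248 for 12–32, 224 for 36–56, 200 for 60–80, 176 for 84–104.

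**Elapsed weeks from each site visit to the later assessments**

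| First up-titrated dose | Elapsed weeks |
|---|---|
| 156 | 24, 52, 76, 104 |
| 168 | 12, 40, 64, 92 |
| 180 | 28, 52, 80 |
| 192 | 16, 40, 68 |
| 208 | 24, 52 |
| 220 | 12, 40 |
| 232 | 28 |
| 244 | 16 |

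**Starts that can contribute to each interval**

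| Interval (weeks) | Of 8 site visits | Of 26 four-weekly doses (156–256) |
|---|---|---|
| 4–8 | 0 | 8 |
| 12–32 | 8 | 22 |
| 36–56 | 6 (156–220) | 17 |
| 60–80 | 4 (156–192) | 11 |
| 84–104 | 2 (156, 168) | 6 |

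The right-hand column covers starts off the scheduled site visits, for example in subjects who attend every four weeks because they cannot self-inject. The shrinkage runs from 12–32 weeks onward. The 4–8 week point is a sparse, separate group.

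**Share of escalators able to contribute, 12–32 through 84–104.** The documents do not give the timing, so three assumed patterns over the 8 visits are shown:
- even: 100, 75, 50, 25%
- front-loaded (50, 20, 10, 8, 5, 4, 2, 1%): 100, 97, 88, 70%
- back-loaded (2, 4, 8, 10, 16, 20, 20, 20%): 100, 60, 24, 6%

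**Size of a pure cohort artefact.** Assume even timing, a response for each subject that stays constant after escalation, an overall mean of 50%, and response linear in escalation week. Let f = (mean contributing week − 156)/(244 − 156):
- 12–32: mean week 1600/8 = 200, f = 0.500
- 36–56: 1124/6 = 187.3, f = 0.356
- 60–80: 696/4 = 174, f = 0.205
- 84–104: 324/2 = 162, f = 0.068

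Drift from first to last = gap × (0.500 − 0.068) = gap × 0.432.
- Latest escalators 20 points below the earliest: 50.0, 52.9, 55.9, 58.6%, a false gain of 8.6 points.
- 10-point gap: 4.3 points.
- Gaps reversed: false losses of 8.6 and 4.3.
- No gap: 0.

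In the fixed cohort of starts at Weeks 156 and 168 the drift is 0 in every one of these scenarios.

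**The case against.** **The outputs are exploratory and partly protected.** SAP 4 labels the results exploratory, and no dose comparison is planned. The ACR shift tables pair each subject with his or her own earlier visit, individual listings are planned, and binary summaries carry counts. This stands in part: within the three paired intervals the ACR reader has a proper reference. But nothing pairs ACR at 84–104 weeks, the most selected interval, or HAQ-DI at any interval. Pairing within an interval also does not make different intervals comparable.

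**Timing is not purely clinical.** Amendment 1 reports status at 6 September 2015 and needed ethics approval before implementation. Subjects with a core baseline before about September 2012 (156 weeks earlier) were already past Week 156 by then. Escalation week therefore depends partly on enrolment date and site approval, which may be only weakly related to response. This stands. It could reduce the artefact, and it could leave few subjects starting by Week 168.

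**The size is an illustration.** This also stands. The documents give no number, timing or response of escalators.

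**Readings the documents do not support.** A reader might infer one pooled line across all doses. SAP 12.4 specifies no such line, and SAP 5.1 separates the 75–150, 75–300 and 150–300 mg sequences. Nor does 12.4 state the axis of the line plots; the intervals come from 17.1. A reader might also infer that the plots must show a false loss or gain, but without a response gradient by escalation time there is none. Finally, not all follow-up stops at Week 260; only the ACR and HAQ-DI assessments do.

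**Conclusion.** The concern holds as a structural point. Once any subject in a sequence escalates after Week 176, the 84–104 week interval cannot represent the same people as the earlier ones, and the SAP sets no fixed cohort or minimum follow-up for these tables and figures. That follows from the visit schedule alone.

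Whether a visible trend results depends on response varying with escalation time. The 8.6-point and 4.3-point figures rest on assumed even timing, constant individual response and a linear gradient. They show plausible scale, not expected bias, and the sign is open.

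The SAP already uses the needed ideas elsewhere in 12.4: an X-ray completer analysis, and a minimum of more than 8 weeks since up-titration for the Sankey-style chart. The change is worth making before reporting. It does not call the primary by-visit ACR summaries into question.

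**What to change.** In the post-up-titration ACR and HAQ-DI outputs, within each dose sequence:

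1. For every interval, show n and the pre-up-titration value of the same subjects. This also exposes selective loss, since the protocol tells investigators to discontinue subjects who do not benefit.
2. Add one line for a fixed cohort with a scheduled assessment in every interval joined: first up-titrated dose by Week 168 for 12–32 through 84–104 weeks, or by about Week 192 for 12–32 through 60–80. In the second case check each start week, because on the four-weekly grid a start at 172 has no assessment in 12–32 and a start at 176 none in 60–80.
3. Where that cohort is too small, show unjoined points and footnote that the subjects change between intervals.

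The cost is a few extra rows and one added line. The drawback is size: under even timing the Week 168 cohort is 25% of escalators, split further by dose sequence. The cohort removes the effect of staggered starts but not of later dropout, for which item 1 is needed. Replacing every line by several timing cohorts per sequence would spread the subjects too thinly and is not needed.

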5.5.6 Rescue medication

Rescue medication is defined as any new therapeutic intervention or a significant change to ongoing therapy made because a subject is experiencing either no benefit from participation in the trial or worsening / exacerbation of their disease. Serious consideration should be given to withdraw subjects who require significant amounts of rescue medication. All medication changes must be recorded in the Prior/ Concomitant medications eCRF page.

Subjects will continue to be on background MTX (if they were already taking MTX at the start of core study CAIN457F2306) throughout the study. The dose of MTX may be adjusted as deemed appropriate and necessary at the investigator's discretion in this extension study.

Any use of rescue medication must be recorded on the corresponding Concomitant Medications eCRF.

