5.5.7 Concomitant treatment

The investigator should instruct the subject to notify the study site of any new medications he/she takes after enrollment into the study. All medications, procedures and significant non-drug therapies (including physical therapy and blood transfusions) administered after enrollment must be recorded on the Concomitant medications Dose Administration Record in the CRF.

Methotrexate

In subjects on MTX , dose of MTX (≤ 25 mg/week) may be adjusted as deemed appropriate and necessary at the investigator's discretion.

Folic acid

Subjects taking MTX must also be taking folic acid supplementation during the trial to minimize the likelihood of MTX associated toxicity. Folic acid supplementation should not be taken on the same day of MTX intake.

Systemic corticosteroids

The dose and regimen of systemic corticosteroids (oral or intramuscular) may be modified as deemed appropriate and necessary and as per investigator's judgment and subject need. Any change in the dose of systemic corticosteroids during the trial must be recorded on the corresponding eCRF page.

Intra-articular corticosteroids

As per investigator's judgment and subject need, intra-articular corticosteroid injections can be performed. The total dose administered must be recorded on the corresponding eCRF page.

Non-steroidal anti-inflammatory drugs (NSAIDs) (including COX-1 or COX-2 inhibitors) and acetaminophen/paracetamol

Subjects taking NSAIDs, low strength opioids or paracetamol/acetaminophen PRN can continue to do so in the study; however, they must refrain from any intake during at least the 24 hours before a visit with disease activity assessment. Any change of the NSAID / paracetamol / acetaminophen treatment during the trial should be recorded on the corresponding eCRF page.

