NSAID	Non-Steroidal Anti-Inflammatory Drug
NovDTD	Novartis Drug/Therapy Dictionary
████	████████████████████
PDS	Programming and Dataset Specifications
PFS	Pre-filled Syringe
PK	Pharmacokinetic
PoC	Proof of Concept
PRO	Patient Reported Outcome
PsA	Psoriatic Arthritis
QoL	Quality of Life
RA	Rheumatoid Arthritis
RBC	Red blood cells
RDC	Remote Data Capture
RF	Rheumatoid Factor
SAE	serious adverse event
s.c.	Subcutaneous
████	██
SJC	Swollen joint count
SpA	Spondyloarthritis
SUSAR	Suspected Unexpected Serious Adverse Reaction
TJC	Tender joint count
TNF	Tumor Necrosis Factor
TNF α -IR	TNF α Inhibitor Incomplete/Inadequate Responders
ULN	Upper Limit of Normal
UPT	Urine Pregnancy Test
VAS	Visual Analog Scale

WBC White blood cells

1 Introduction

Data will be analyzed by Novartis according to the data analysis section 9 of the study protocol. That statistical methodology is described below and any deviations from the protocol are documented. Additional detailed information regarding the analysis methodology is contained in the Appendix section.

2 Changes to statistical methods planned in the protocol

No multiple imputation techniques and no MMRM estimation will be performed due to the presence of up-titrators.

[figure not shown]
3 Study objectives

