3.1 Primary objectives

To evaluate the long-term efficacy of secukinumab with respect to ACR20, ACR50 and ACR70 response over time up to Week 260 in subjects with active PsA and who complete the phase III study CAIN457F2306.

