12.3 Handling of missing data

For primary analysis, data will be presented using all observed data at the given time point of analysis.

No multiple imputation or Mixed Models for Repeated Measures (MMRMS) will be considered since the influence of up-titrators in each group population violates the MAR assumption.

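### The primary ACR20/50/70 rates count values recorded after rescue medication, and no visible planned analysis shows how many of the responses came after rescue

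*SAP*

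**What the plan says.** **Analysis.** SAP 12.3 sets the data rule: "For primary analysis, data will be presented using all observed data at the given time point of analysis". SAP 12.4 applies it to every efficacy variable: "All the above efficacy variables will be analyzed on the FAS (unless otherwise specified) for all applicable analysis visits based on the observed data". SAP section 2 removes the model-based alternatives: "No multiple imputation techniques and no MMRM estimation will be performed due to the presence of up-titrators". The SAP gives rescue no role in that decision. The objective in SAP 3.1 is "To evaluate the long-term efficacy of secukinumab with respect to ACR20, ACR50 and ACR70 response over time up to Week 260".

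**Treatment after entry.** Protocol 5.5.6 says: "Rescue medication is defined as any new therapeutic intervention or a significant change to ongoing therapy made because a subject is experiencing either no benefit"; the other ground it names is disease that is getting worse. It must be recorded. On consequences the same section says: "Serious consideration should be given to withdraw subjects who require significant amounts of rescue medication". That asks for a judgement and does not define a significant amount.

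Protocol 3.1, 5.5.6 and 5.5.7 let the investigator adjust methotrexate and start or change corticosteroids. On joints, 5.5.7 says: "As per investigator's judgment and subject need, intra-articular corticosteroid injections can be performed". A 24-hour abstention before disease activity assessments applies to NSAIDs, low-strength opioids and paracetamol; none is stated for steroids. Table 5-1 prohibits other biologics, other investigational treatment and live vaccines.

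**Where co-medication appears in the SAP.** Section 11 tabulates concomitant psoriatic arthritis therapy by group. Sections 6 and 12.4 show ACR response by concomitant methotrexate use. Section 12.4 also provides individual listings of ACR components and responses.

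**The concern.** Protocol 3.4 confirms that there is no placebo or active comparator, so the ACR rates over time are read at face value. By definition, rescue goes to subjects who are doing badly. If it works, some of them become responders, and the observed-data rule credits that response to secukinumab.

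The SAP already accepts that a change of treatment made for inadequate control complicates interpretation. For dose escalation it defines separate treatment sequences, shift tables and post-escalation summaries (SAP 5.1, 12.4 and 17.1). Rescue medication, which is also given for inadequate control, gets nothing comparable.

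At stake is whether a reader of the long-term rates can tell response on secukinumab alone from response on secukinumab plus rescue. After Week 156 the ACR components are scheduled only at Weeks 180, 208, 232 and 260 (Tables 6-2 and 6-3), so each later time point rests on a single assessment.

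**Working it through.** **The plan's own figure.** The only planning number is the expected enrolment in Protocol 9.7: 320 + 140 = 460 and 360 + 160 = 520. It reproduces exactly and does not bear on this point. There is no power or alpha calculation to affect, and no rescue rate is given.

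**Is there a rule?** SAP 12.1 defines the ACR variables and scales joint counts for joints without data. SAP 12.3 and 12.4 specify observed data. SAP 17.3 gives the interval methods. None of these mentions rescue: there is no non-responder rule, exclusion, flag or sensitivity analysis. Protocol 9.4.4 allowed optional sensitivity analyses, but for missing data.

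**What could the size be?** Among subjects assessed at a visit, let
- p = observed response rate,
- r = share with prior rescue,
- s = response rate among those rescued,
- s0 = the rate the same subjects would have had without rescue.

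Responses recorded after rescue make up r × s of the reported rate. The part caused by rescue is r × (s − s0). If rescue does not reduce response, 0 ≤ s0 ≤ s, so that part lies between 0 and r × s. Counting rescued subjects as non-responders gives p − r × s.

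For p, take the Week 104 ACR50 rates in the Amendment 1 rationale: 46.4% (150 mg) and 35.5% (75 mg). Both r and s are assumptions, with s from 30% to 60%.

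| r | r × s (points) | 46.4% becomes | 35.5% becomes |
|---|---|---|---|
| 5% | 1.5 to 3.0 | 44.9 to 43.4 | 34.0 to 32.5 |
| 10% | 3.0 to 6.0 | 43.4 to 40.4 | 32.5 to 29.5 |
| 20% | 6.0 to 12.0 | 40.4 to 34.4 | 29.5 to 23.5 |

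**Scale.** The SAP 17.3.2.1 score interval with continuity correction has limits

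L = [2np + z² − 1 − z√(z² − 2 − 1/n + 4p(n(1−p) + 1))] / [2(n + z²)]

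U = [2np + z² + 1 + z√(z² + 2 − 1/n + 4p(n(1−p) − 1))] / [2(n + z²)]

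With n = 230 per dose group (460/2, an assumed even split) and z = 1.96, the 95% interval is 39.9-53.1% around 46.4% and 29.4-42.1% around 35.5%. The half-widths are (53.1 − 39.9)/2 = 6.6 and (42.1 − 29.4)/2 = 6.35 points. The larger entries in the table are therefore of the same order as, or larger than, the sampling error that will be displayed.

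**Injected joints.** Suppose 10 swollen joints at baseline and 9 now, an improvement of (10 − 9)/10 = 10%. If an injection clears one joint and it is scored absent, the count is 8 and the improvement is 20%, which meets the ACR20 swollen-joint criterion. If that joint is instead marked not applicable and the count is scaled as in SAP 12.1, it is 76 × 8/75 = 8.11 and the improvement is 18.9%, which does not. The visible text does not say which applies.

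**The case against.** The strongest reply is that this is a descriptive, uncontrolled extension with no hypotheses and no planned dose comparison (Protocol 9.4.2). Using observed values whatever else the subject takes is a legitimate treatment-policy summary. That stands, and it is why the observed analysis should stay. It does not answer the point that the SAP never names the strategy and plans nothing to show how much response follows rescue.

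The plan is also not silent on co-medication: it has the methotrexate subgroup, the concomitant-therapy table and the listings. None of them connects a change made for worsening to response at a given visit.

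Several stronger readings are tempting and are not supported:
- **That the rates are inflated by a known amount.** No rescue rate is given. The product r × s includes subjects who responded before rescue or would have responded anyway.
- **That the bias grows with time.** Entrants must be judged to benefit (Protocol 4.1 and 4.2), investigators should stop treatment in those not benefiting (3.1 and 5.5.9), and poorly controlled subjects should be escalated in the open-label period after Amendment 1 (3.1 and 5.2). These act against accumulation, and the documents do not show the net effect.
- **That conventional DMARDs may expressly be added.** This is inferred from the rescue definition and from their absence from Table 5-1. Another biologic does require stopping study treatment.
- **That an injected joint is scored as clear.** Protocol 6.4.1.1 offers a not-applicable box. One joint also cannot decide ACR20 alone, since the tender-joint criterion and three of five other measures must be met too.

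Finally, text near the joint-count rules is redacted, SAP 12.2 is not in the text available, and further concomitant-medication rules are deferred to the programming specifications (SAP section 11). If a rule for rescue sits there, citing it in the SAP would settle the point.

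**Conclusion.** The concern holds as a gap in the analysis plan. The primary ACR20/50/70 rates include values recorded after rescue, and nothing visible links rescue to response by visit. With no control arm and an objective worded as efficacy of secukinumab, those responses will be credited to the drug.

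The direction is probably upward, because rescue is given to subjects who are doing poorly. The size is unknown. The 1.5-12 points rest wholly on assumed values of r (5-20%) and s (30-60%) and are an upper bound on the effect of rescue. They show only that the issue could matter beside interval half-widths of about 6.5 points. No error rate or sample size is affected.

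**What to change.** In SAP 12.3 and 12.4:

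1. Keep the observed-data analysis as primary, and state that it uses values regardless of rescue medication.
2. At each extension visit, report the number and percentage of ACR20, ACR50 and ACR70 responders with prior recorded rescue.
3. Add one supplementary ACR20/50/70 analysis on the same visits, counting a subject as a non-responder at every visit after the first therapy that meets the Protocol 5.5.6 definition.
4. Settle which medication changes qualify by a medical review of the concomitant-medication records, done without sight of ACR results. The definition turns on the reason for the change and on whether it was significant, so the criteria should be written down beforehand.

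A rule carrying forward the pre-injection status of an injected joint is not recommended. Protocol 5.5.7 requires only the total dose of intra-articular steroid to be recorded, so the joint may not be identifiable. Injections given for worsening are already covered by item 3.

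**Cost.** SAP text, one derived flag and the medication review. Rescue must already be recorded, and no treatment rule changes. The supplementary rate is conservative: a single rescue soon after Week 104 counts as non-response up to Week 260. It should be presented as a lower bound beside the observed rate, not as a replacement for it.
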